1.0 PROTOCOL SYNOPSIS

STUDY NAME	First – in – man study to assess the safety and feasibility of the Bashir™ Endovascular Catheter for the treatment of acute pulmonary embolism.
PROTOCOL NO.	THRO-CLIN-2018-01
PROTOCOL DATE	September 14, 2019
SPONSOR	Thrombolex, Inc. New Britain, PA
CO-PRINCIPAL INVESTIGATORS	[name] MD – Interventional Cardiologist [name] MD – Interventional Radiologist
STUDY DEVICE	The Bashir™ Endovascular Catheter is a device intended for the localized infusion of therapeutic agents into the pulmonary artery and peripheral vasculature.
THROMBOLYTIC ADMINISTRATION	
Pulse Sprays: r-tPA 2mg in 20cc 0.9% NaCl divided into two (2) 10cc syringes to administer in two (2) pulse sprays, 10cc each, through the basket infusion port with 10cc syringes.
 
Unilateral PE: 2mg total in 20cc administered in two (2) 10cc syringes.
 
Bilateral PE: 4 mg total in 40cc administered in two (2) 10cc syringes into each PA for a total of four (4) syringes, two (2) into each PA.
 
Infusion:
 
Unilateral PE: r-tPA 10mg in 750cc 0.9% NaCl infused at 1.27mg/hr at an infusion rate of 95cc/hr, through the Bashir™ Endovascular Catheter until complete. Total r-tPA dose (pulse spray and infusion) is 12.0mg.
 
Bilateral PE: r-tPA 5mg in 500cc 0.9% NaCl infused at 0.65mg/hr at an infusion rate of 65cc/hr bilaterally through each Bashir™ Endovascular Catheter, until complete for a total r-tPA dose of 1.3mg/hr, 0.65mg per hour through each catheter. Total r-tPA dose (pulse spray and infusion) is 14.0mg.

ANTICOAGULANT DOSAGE AND ADMINISTRATION	
Pre-procedure: Unfractionated heparin will be administered IV to prolong the aPTT pre-procedure (suggested range 60-80 seconds).
 
Note: Use of enoxaparin (Lovenox®) is permitted pre-procedure for the treatment of PE. If Lovenox is given, then catheter directed thrombolysis procedure is to start no sooner than 12 hours after the last Lovenox dose was administered.
 
Procedure: Heparin infusion will be discontinued upon arrival in the IR/Cath lab. ACT will be monitored in IR/Cath Lab and heparin boluses administered to achieve ACT \geq 200 seconds.
 
During r-tPA Infusion: Heparin infusion will be restarted post-procedure and administered through the side arm of each sheath to prolong the aPTT (suggested range 40-60 seconds).
 
Post r-tPA Infusion: Upon completion of r-tPA infusion, maintain patency through the BEC by replacing r-tPA with heparinized saline TKO using the infusion pump. Starting 45 minutes (\pm 15 minutes) after the r-tPA completion, administer Lovenox 1mg/kg sub-Q every 12 hours (\pm30 minutes) through the completion of the 48-hour CTA.

1.0 PROTOCOL SYNOPSIS (CONTINUED)

POPULATION	Patients 18 years of age or older who present with symptoms of acute submassive PE within 14 days of onset of symptoms will be considered for this study.
STUDY DESIGN	Prospective, non-randomized, multi-center study.
STUDY OBJECTIVE	Assess the safety and feasibility of the Bashir™ Endovascular Catheter for the administration of low dose thrombolytic for acute submassive pulmonary embolism.
SAMPLE SIZE	Up to ten (10) subjects will be enrolled and treated.
SITES	Up to five (5) sites will be qualified to participate in this study.
PRIMARY ENDPOINTS	
1. Safety: Major bleeding, as defined by International Society of Thrombosis and Hemostasis (ISTH), within 72 hours of initiation of r-tPA administration. Bleeding criteria are as follows: Major Bleeding in Non-Surgical Patients
 
 a. Fatal bleeding; and/or b. Symptomatic bleeding in a critical area or organ, such as intracranial, intraspinal, intraocular, retroperitoneal, intraarticular or pericardial, or intramuscular with compartment syndrome; and/or c. Bleeding causing a fall in hemoglobin level of 2 g/dL (1.24 mmol/L) or more or leading to transfusion of two or more units of whole blood or red cells. 
2. Feasibility: Device success defined as the ability to use the Bashir™ Endovascular Catheter as described in this protocol.

SECONDARY ENDPOINTS	
1. All-cause mortality at hospital discharge through 30-day follow-up.
 
2. SAEs through 30-day follow-up.
 
3. Anticipated (non-serious) adverse events (AEs) through 30-day follow-up.
 
4. Recurrent PE through 30-day follow-up.
 
5. Clinically Relevant Non-Major bleeding: Any sign or symptom of hemorrhage (e.g. more bleeding than would be expected for a clinical circumstance, including bleeding found by imaging alone) that does not fit the criteria for the ISTH definition of major bleeding but does meet at least one of the following criteria:
 
 a. Requiring medical intervention by a healthcare professional. b. Leading to hospitalization or increased level of care. c. Prompting a face to face (i.e., not just a telephone or electronic communication) evaluation. 
6. Technical procedural complications.
 
7. RV/LV end diastolic diameter ratio at 24 hours after completion of r-tPA infusion compared to baseline, by echocardiogram.
 
8. RV/LV diameter ratio at 48 hours after completion of r-tPA infusion, by contrast-enhanced chest CTA compared to baseline.

Continued on next page

1.0 PROTOCOL SYNOPSIS (CONTINUED)

SECONDARY ENDPOINTS (CONTINUED)	
 9. Modified Miller Index at 48 hours post completion of the r-tPA infusion as compared to baseline by contrast-enhanced chest CTA. 10. Systolic PA pressure measured at completion of infusion and compared to baseline. 11. Cardiac output (CO by modified Fick calculation) and cardiac index (CI) following completion of infusion, upon return to the IR suite/Cath lab compared to baseline.
ELIGIBILITY CRITERIA	
Inclusion Criteria
 
 1. Willing and able to provide informed consent; 2. 18 years of age and less than 75 years of age; 3. PE symptom duration \leq 14 days; 4. Filling defect in at least one main or lobar pulmonary artery as determined by contrast enhanced chest CT; 5. RV/LV diameter ratio \geq 0.9 by CTA as determined by the investigative site; 6. Willing and able to comply with all study procedures and follow-up. 
Exclusion Criteria
 
 1. Cerebrovascular Accident (CVA) or transient ischemic attack (TIA) within one (1) year; 2. Head trauma, or other active intracranial, or intraspinal disease within one (1) year; 3. Recent (within one month) or active bleeding from a major organ; 4. Intracranial condition(s) that may increase the risk of bleeding (e.g., neoplasms, arteriovenous malformations, or aneurysms); 5. Patients with bleeding diathesis; 6. Hematocrit < 30%; 7. Platelets < 100,000/μL; 8. INR > 1.5; 9. aPTT > 50 seconds in the absence of anticoagulants; 10. Major surgery within fourteen (14) days; 11. Serum creatinine > 2.0 mg/dL; 12. Clinician deems high-risk for catastrophic bleeding; 13. History of heparin-induced thrombocytopenia (HIT); 14. Pregnancy; 15. Systolic blood pressure < 90 mmHg for > 15 minutes; 16. Any vasopressor support; 17. Cardiac arrest (including pulseless electrical activity and asystole) requiring active cardiopulmonary resuscitation (CPR); 18. Evidence of irreversible neurological compromise; 19. Life expectancy < one (1) year; 20. Use of thrombolytics or glycoprotein IIb/IIIa antagonists within 3 days prior to inclusion in the study; 
Continued on next page

1.0 PROTOCOL SYNOPSIS (CONTINUED)

ELIGIBILITY CRITERIA (CONTINUED)	
21. Use of non-vitamin K oral anti-coagulants (NOACs), such as rivaroxaban, apixaban, dabigatran, edoxaban within 48 hours prior to inclusion in the study;
 
22. Use of enoxaparin sodium injection (Lovenox®) within 12 hours of procedure start time;
 
23. Profound bradycardia requiring a temporary pacemaker and/or inotropic support;
 
24. Previous enrollment in this study;
 
25. Morbidly obese (BMI >45 kg/m²) patient who by the judgement of the investigator is high risk for bleeding;
 
26. Absolute contraindication to anticoagulation;
 
27. Uncontrolled hypertension;
 
28. Currently participating in another study;
 
29. In the opinion of the investigator, the subject is not a suitable candidate for the study.

SUBJECT PARTICIPATION	Duration of participation will be from time of informed consent through 30-day follow-up.
STUDY DURATION	It is estimated that the study duration will be eleven (11) months.
DATA SAFETY MONITOR	[name] MD, MS Brigham and Women's Hospital Boston, MA
STUDY MANAGEMENT	Eminence Clinical Research, Inc. [name]
DATA MONITORING	
EDC	
CTA / ECHO INDEPENDENT CORE LAB	Medical Metrics, Inc. [name]

3.0 TERMS AND DEFINITIONS

TERM	DEFINITION
AE	Adverse Event - An adverse event is any untoward medical occurrence associated with the use of a drug in humans, whether or not considered drug related (21 CFR 312.32(a)).
aPTT	Activated Partial Thromboplastin Time
BEC	Bashir™ Endovascular Catheter
BNP	Brain Natriuretic Peptide is made inside the pumping chambers of the heart when pressure builds up from heart failure. The test is an important to diagnose heart failure quickly.
BSA	Body Surface Area - Du Bois formula: $BSA = 0.007184 \times W^{0.425} \times H^{0.725}$ Du Bois D, Du Bois EF (Jun 1916). A formula to estimate the approximate surface area if height and weight are known. ²¹ This formula is not required if sites have ability to calculate BSA per other standard method.
CBC	Complete Blood Count
CFV	Common Femoral Vein
CI	Cardiac Index: Hemodynamic parameter that relates the cardiac output (CO) from right or left ventricle in one minute to body surface area (BSA), thus relating heart performance to the size of the individual. The unit of measurement is liters per minute per square meter (L/min/m ²). CI = CO/BSA.
CO	Cardiac Output
CMP	Complete Metabolic Panel
CTA	Computerized Tomography Angiogram
DUS	Duplex Ultrasound- a type of ultrasound used to visualize the vasculature. This is a study requirement to assess the ability to access the PA(s) from the CFV.
DSM	Data Safety Monitor: Physician experienced in the treatment of PE with mechanical thrombolysis will adjudicate all adverse events in this study.
GTT	Drip
Modified Fick Calculation	$CO = \frac{O_2 \text{ Consumption (VO}_2\text{) ml/min}}{(CaO_2 - CvO_2) \times 10}$ $VO_2 = 125 \times BSA$ $CaO_2 = (1.36 \times Hgb \times SaO_2)$ $CvO_2 = (1.36 \times Hgb \times SvO_2)$ 
This Modified Fick calculation is required in this protocol.

3.0 TERMS AND DEFINITIONS (CONTINUED)

HIT	Heparin Induced Thrombocytopenia
Hrs	Hours
IJ	Internal Jugular
INR	International Normalized Ratio
LCFV	Left Common Femoral Vein
Modified Miller Index (MMI)	To define the CT obstruction index, the arterial tree of each lung is regarded as having 10 segmental arteries (3 to the upper lobes, 2 to the middle lobe and the lingula, and 5 to the lower lobes). The presence of embolus in a segmental artery is scored 1 point, and emboli in the most proximal arterial level are scored a value equal to the number of segmental arteries arising distally. To provide additional information about the residual perfusion distal to the embolus, a weighting factor is assigned to each value, depending on the degree of vascular obstruction. This factor is equal to zero, when no thrombus is observed; 1, when partially occlusive thrombus is observed; or 2, with total occlusion. Thus, the maximal CT obstruction index is 40 per patient. ²²
PAD	Pulmonary Artery Diastolic Pressure
PaO₂	Partial Pressure of Arterial Oxygen
PAP	Pulmonary Artery Pressure
PAS	Pulmonary Artery Systolic Pressure
PE	Pulmonary Embolism
PMCDT	Pharmaco-Mechanical Catheter Directed Thrombolysis
Procedure Start Time	Procedure start time refers to the PMCDT (BEC) procedure and is defined as the injection of local anesthetic at the access site prior to sheath placement in the IR Suite/Cath Lab.
RCFV	Right Common Femoral Vein
Recurrent PE	Recurrent PE is defined as symptomatic and objectively confirmed with contrast-enhanced chest CT or invasive contrast pulmonary angiography.
RV/LV	Right Ventricular / Left Ventricular
SAEs	
Serious Adverse Event - An adverse event or suspected adverse reaction is considered "serious" if, in the view of either the investigator or sponsor, it results in any of the following outcomes:
 
 1. Death 2. Life-threatening adverse events

Continued on next page

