6.2.2 Secondary Endpoints

1. All-cause mortality at hospital discharge through 30-day follow-up.
2. SAEs through 30-day follow-up.
3. Anticipated (non-serious) adverse events (AEs) through 30-day follow-up.
4. Recurrent PE through 30-day follow-up.
5. Clinically Relevant Non-Major bleeding: Any sign or symptom of hemorrhage (e.g. more bleeding than would be expected for a clinical circumstance, including bleeding found by imaging alone) that does not fit the criteria for the ISTH definition of major bleeding but does meet at least one of the following criteria:
 - a) Requiring medical intervention by a healthcare professional.
 - b) Leading to hospitalization or increased level of care.
 - c) Prompting a face to face (i.e., not just a telephone or electronic communication) evaluation.
6. Technical procedural complications.
7. RV/LV end diastolic diameter ratio at 24 hours after completion of r-tPA infusion compared to baseline, by echocardiogram.

8. RV/LV diameter ratio at 48 hours after completion of r-tPA infusion, by contrast enhanced chest CTA compared to baseline.
9. Modified Miller Index at 48 hours post r-tPA infusion as compared to baseline by contrast enhanced chest CTA.
10. Systolic PA pressure measured at completion of infusion and compared to baseline.
11. Cardiac output (CO by modified Fick calculation) and cardiac index (CI) following completion of the r-tPA infusion compared to the baseline. Please refer to Terms and Definitions section for the modified Fick calculation to be done in the IR suite/Cath lab.

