10.4 Tests Required 48 Hours Following End of r-tPA Infusion

10.4.1 Imaging

1. **Contrast Enhanced CTA of the Chest** – A contrast enhanced chest CTA will be performed at 48 hours (± 6 hours) after completion of the r-tPA infusion. The contrast enhanced chest CTA is used to determine the post-procedure RV/LV diameter ratio and Modified Miller Index Score. Please note that subject must be on Lovenox 1mg/kg every 12 hours through the completion of the 48-hour CTA. *The CT will be sent to the core lab for analyses.*

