12.1 Bashir Endovascular Catheter Anticipated Adverse Events

Table 3. Anticipated Adverse Events Related to the Investigational Device¹⁸

Adverse Event	Definition
Allergic reactions	Any exaggerated immune response to a foreign antigen regardless of mechanism
Hematoma at access site	Blood collects under the skin in the area where the physician accessed the femoral artery to perform the treatment, and results in bruising (ecchymosis)
Hemorrhage	A profuse discharge of blood from a ruptured blood vessel resulting in a decrease in hemoglobin
Intimal damage	Trauma to the intimal lining of the vessel
Ischemia	Inadequate blood supply to an organ or part of the body or heart muscles
Pain and tenderness	Discomfort in an area that is impacted by the device
Vascular thrombosis	A formation of a blood clot in an artery or vein
Vessel perforation	A hole or tear in an artery or vein
Vessel spasm	A temporary tightening (constriction) of the muscles in the wall of one of the arteries that supplies blood flow

12.2 r-tPA Anticipated Adverse Events

Table 4. Anticipated Adverse Events Related to r-tPA Infusion¹⁵

Adverse Event	Definition
Fever	Elevated temperature above normal
Hematuria	Blood in the urine
Hematoma	Collection of blood under the skin
Hemoptysis	Coughing up blood
Hypotension	Sustained low blood pressure, below normal (Usually indicative of MAP< 60 mmHg)
Mucosal bleeding	Bleeding in the mouth
Pleural effusion	Fluid accumulation around the lung
Pulmonary edema	Fluid accumulation in the tissue and air spaces of the lungs
Pulmonary re-embolization	Sudden blockage of a major blood vessel
Thromboembolism	Obstruction of a blood vessel by a clot that has become dislodged

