13.5 Investigator SAE Reporting Requirements

An SAE occurring during the study or within 30 days of stopping the treatment must be reported to the study safety monitor. Any such SAE due to any cause, whether or not related to the study medication, must be reported within 24 hours of occurrence or when the investigator becomes aware of the event.

The investigator must send a preliminary report of any such SAE to the project manager via the EDC system within 24 hours or if this is not possible via email or fax using an SAE Report Form, or at a minimum by telephone.

The event must be recorded on the electronic SAE CRF page. Preliminary reports of SAEs must be followed by detailed descriptions, including clear pseudonymized photocopies of hospital case reports, consultant reports, autopsy reports, and other documents when requested and applicable. All photocopies should be redacted to remove patients' personal details and annotated with the patient's unique study identifiers. SAE reports must be made whether or not the investigator considers the event to be related to the investigational drug. Appropriate remedial measures should be taken to treat the SAE, and the response to treatment should be recorded. Patients must be closely followed until sufficient information is obtained to indicate a return to normal status or until the event stabilizes at a level acceptable to the investigator.

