17.0 DATA SAFETY MONITOR

A data safety monitor will be selected to review the study conduct, feasibility data, and safety data and will adjudicate all types of adverse events reported in this study. The independent DSM shall have the final adjudication for the events. A data safety charter will be established and will be approved by the data safety monitor. Qualifications for the DSM, at a minimum, shall include current experience with catheter directed thrombolysis for the treatment of massive and submassive pulmonary emboli, management of the patient post-treatment and extensive research experience. Adherence to the study stopping criteria in this protocol will also be included in the DSM meetings in addition to following the charter.

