18.2 Safety Study Stopping Rule

If two (2) patients undergoing the investigational procedure die or experience an unprovoked intracranial hemorrhage, confirmed by independent DSM adjudication, and did not have a protocol violation such that he/she cannot be considered as representative of the intended patient population, the study shall be paused for re-evaluation, and may be stopped.

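### The recurrent PE definition has no autopsy route, so a fatal recurrence proven only at autopsy would, read literally, not count toward secondary endpoint 4

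*Combined protocol and SAP*

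**What the plan says.** Section 3.0 gives the definition: "Recurrent PE is defined as symptomatic and objectively confirmed with contrast-enhanced chest CT or invasive contrast pulmonary angiography". The endpoint in Section 6.2.2, item 4, reads "Recurrent PE through 30-day follow-up". Neither that item nor the synopsis adds another means of confirmation.

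Four other places bear on how a fatal case would be handled:

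- Section 6.2.2, item 1, counts deaths from any cause: "All-cause mortality at hospital discharge through 30-day follow-up". No endpoint is specific to PE death.
- Section 13.5 lists among the SAE follow-up documents "consultant reports, autopsy reports, and other documents when requested and applicable". It does not link them to endpoint 4.
- Section 17.0 has the DSM adjudicate all reported adverse events and adds: "The independent DSM shall have the final adjudication for the events". It refers to a charter that is not part of the documents.
- Section 12.2, Table 4, lists pulmonary re-embolization as an anticipated r-tPA event, described as "Sudden blockage of a major blood vessel", with no imaging condition.

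**The concern.** Both accepted confirmations need a patient who lives long enough to reach a scanner or a catheter laboratory. Autopsy is also an objective confirmation, and the protocol already expects to receive autopsy reports, but the definition gives them no role in this endpoint. The omission can only lower the recurrent PE count, and it does so for the most severe form of the event, so any error favours the device.

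Scheduled imaging does little to close the gap. Section 10.4.1 says "A contrast enhanced chest CTA will be performed at 48 hours" after the infusion ends. Sections 10.7 and 11 schedule no chest CT at discharge or at 30 days. For most of the follow-up window, confirmation therefore depends on the patient surviving to a scan prompted by symptoms.

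At stake is whether one safety-related secondary count is correct. There is also a carry-over risk: Section 16.1 says the study should help refine endpoints before a pivotal trial, where the same definition would matter more.

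**Working it through.** **Nothing to reproduce.** The plan gives no recurrence rate, no assumed event rate and no calculation for this endpoint. Section 16.2 specifies descriptive statistics only. The check applies the written rule to cases, then shows what one case does to the count.

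**Step 1. Apply the definition.** The rule is: symptomatic AND (positive contrast chest CT OR positive invasive angiogram). A sudden collapse is taken to satisfy the symptom condition.

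| Case within 30 days | Imaged in life? | Counts as written? | Objectively confirmed new PE? |
|---|---|---|---|
| A. Symptoms, positive CT | Yes | Yes | Yes |
| B. Death before imaging; autopsy shows a new embolus | No | No | Yes |
| C. Death before imaging, no autopsy; DSM attributes it to PE | No | No | No |
| D. Death before imaging; autopsy shows only the index thrombus | No | No | No |

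The written rule and objective confirmation disagree only in case B.

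**Step 2. Effect of one case B among 10 subjects.** The sample size of 10 is from Section 16.1. The plan specifies no intervals; exact (Clopper-Pearson) 95% limits are added here for scale.

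- Counted as written, 0/10 = 0%. Lower limit 0; upper limit 1 − 0.025^(1/10) = 0.308, or 30.8%.
- With autopsy accepted, 1/10 = 10%. Lower limit 1 − 0.975^(1/10) = 0.0025, or 0.3%. The upper limit solves (1 − p)^10 + 10p(1 − p)^9 = 0.025, giving p = 0.445, or 44.5%.

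**Step 3. How likely is such a case?** The documents do not say. Assuming a per-patient risk p, the chance of at least one in 10 is 1 − (1 − p)^10:

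- p = 1%: 1 − 0.99^10 = 9.6%
- p = 2%: 1 − 0.98^10 = 18.3%
- p = 5%: 1 − 0.95^10 = 40.1%

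These risks are assumptions chosen to show a range.

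**Step 4. Test a simple autopsy clause against case D.** Every subject enters with PE, and Section 4.3 notes that 74% of the clot burden remained after the highest-dose arm of a cited study. A clause that accepted any PE found at autopsy would count case D as a recurrence. A clause that requires a new embolus distinct from the index thrombus counts B and leaves D out.

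**The case against.** The strongest case on the other side has four parts.

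- **The event is still captured.** A fatal recurrence enters all-cause mortality (endpoint 1) and SAEs (endpoint 2). Adverse events are MedDRA-coded (Section 16.2), and Table 4 offers a term without an imaging condition. The safety stopping rule also counts deaths regardless of PE imaging: "If two (2) patients undergoing the investigational procedure die or experience an unprovoked intracranial hemorrhage". This stands. A reader might infer that a fatal recurrence would disappear from the results or survive only in a narrative, and the documents do not support that. What is missing is its place in endpoint 4.
- **The DSM may resolve it.** A reader might infer that the DSM would be bound to reject an autopsy-proven case. No text says so. The DSM has the last word on events, and the charter could contain a rule. Equally, nothing in the documents lets the DSM set the imaging requirement aside. This limits how certain the consequence is; the definition still needs the missing clause.
- **The sponsor asked for objective confirmation.** A reader might infer that any death attributed to PE should count. That goes against the definition's own standard, and leaving out case C is consistent with it. Only autopsy-proven new PE is a real omission.
- **Little depends on the endpoint.** The study is small, single-group and unpowered, and no stopping rule uses recurrent PE. This stands and sets the weight of the point.

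**Conclusion.** The point holds as a minor correction. As written, the definition leaves out autopsy-proven new PE, and any resulting error lowers the recurrent PE count. One such case changes the result by one subject, 0/10 instead of 1/10, with the intervals shown above.

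This assumes that all 10 subjects are analysed, that the case is the only recurrence, that an autopsy is done and its report obtained, and that no rule in the charter covers it. A reader might also want to state the percentage by which the endpoint is understated. The documents give neither a recurrence rate nor a share of recurrences that are fatal before imaging, so any such figure would only repeat the assumption put in.

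**What to change.** Extend the Section 3.0 definition with a third means of confirmation: *or new pulmonary embolism, distinct from the index thrombus, confirmed at autopsy*. Put the same wording in the DSM charter, and report fatal and non-fatal recurrences separately under endpoint 4. Deaths that the DSM attributes to PE without imaging or autopsy should not enter the confirmed count; list them separately as possible PE-related deaths.

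The cost is one clause in the protocol, matching text in the charter and one extra line in the results table. It uses autopsy reports and adjudication already provided for, and adds no visit, test or change to patient care. The drawback is small: separating a new embolus from residual index thrombus at autopsy needs DSM judgement, and the fatal/non-fatal split lets readers see where that judgement was used.
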